New Mothers. New mothers will be advised that if they consent to participate, they will receive support from peer counselors, information either via paper or mobile (text message and/or video using a mobile phone), and follow-up visits from peer counselors during the 6 months post-delivery. After consent, we will allow mothers to be contacted by one of the trained peer counselors.

Intervention and Data Collection Plan. Peer counselors will have a minimum of 9 visits with mothers. Visit 1 and 2 will occur prenatally at which time baseline data will be collected; initial BF education based on appropriate BEST4Baby content will also take place. The counselors will visit the new mothers within 3-5 days after delivery to obtain relevant data (e.g., when breastfeeding was initiated) and provide needed assistance in establishing BF. Another visit will occur again at two-weeks post-partum to record progress and offer support; remaining visits will be based on an agreed upon schedule. Information will be exchanged at visits and potentially between home visits. BF mothers may request additional visits and peer counselors will be available by phone to answer questions and address concerns. Data will be collected to determine usage of the BEST4Baby app during each visit. Standardized data collection sheets for the peer counselors will be developed; and counselors will be trained in writing field notes and documenting their impressions of the visit. At six months postpartum, research staff will query the mother about present and planned BF practices, environmental influences on breastfeeding, level of community support for BF, and overall satisfaction with the BEST4Baby program. At study conclusion, research staff will obtain feedback from the peer counselors on usability of the mHealth app.

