Comparison Cohort. To enable effect and sample size calculations, an appropriate comparison cohort will be used. We will obtain baseline and six-month post-partum data from a control group of 120 women delivering in facilities and living a suitable distance from study clusters to avoid contamination. A simple survey will be developed and administered by research staff to collect data comparable to that collected from mothers counseled (e.g., current BF practices and future intentions for continuation of breastfeeding). Women in this comparison cohort will provide informed consent and be provided with a small gift (e.g., a branded carrying bag) to show appreciation for their participation.

Month 24

Data Analysis. For survey, application utilization, and subject data associated with Specific Aim 2, we will conduct bivariate analyses (crosstabs, Chi-square procedures) to examine demographics and other measured variables potentially related to breastfeeding. Changes from baseline to follow-up in breastfeeding and other study outcomes and potential moderating variables (e.g., lifestyle changes due to childbirth and behaviors) will be examined.

We will also document engagement in and use of the BEST4Baby program by both the peer counselors and new mothers. The BEST4Baby program will collect usage data, (e.g., utilization, approximate time spent in use of application during home visits) in the follow-up interviews. These combined process measures will be calculated as a _dosage index' and used as a covariate in subsequent analyses. The dosage index will both 1) document process and 2) serve as an independent variable for multivariate modeling. Dosage measures will include time/counts of activity, intensity, engagement, and satisfaction, and will serve to document the feasibility of the BEST4Baby approach to train the peer counselors as well as to support new mothers to initiate and continue breastfeeding.

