We plan to: (1) apply exact logistic regression models to determine if the level of participation in BEST4Baby is associated with an increase in optimal breastfeeding practices, and (2) test mechanisms underlying behavioral outcomes hypothesized in the conceptual model leveraging social cognitive theory, theory of planned behavior, and social marketing. Exact logistic regression models will examine the effect of BEST4Baby dosage, using the dosage index based on pilot test usage and self-report data as independent variables, on 6-month continued breastfeeding. We will calculate odds of exclusive breastfeeding, mixed feeding and use of milk substitutes at follow-up as a function of BEST4Baby dosage based on utilization and process data.

Conclusion: We anticipate that the BEST4Baby program will substantially increase the capacity of the JNMC Women's and Children's Health Research Unit to incorporate mHealth technologies into future use and health care delivery. We plan to utilize findings generated by analysis of BEST4Baby data to develop an application for a fully powered control trial to assess the separate and combined impact of a peer counselor program and mobile applications to support such a program. Cost considerations and greater attention to sustainability will likewise be addressed in that application.

I. Risks to Human Subjects

a. Human Subjects Involvement, Characteristics, and Design

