- Records with contact information and other necessary data to enable participation in research components of the project and the interactions with and between counselors recruited for breastfeeding education/training and mothers who will receive counseling and support during the pilot testing phase of the project

Describe any data that will be collected from human subjects for the project(s) described in the application. Data, primarily qualitative in nature, to be collected from human subjects is listed below.

- Data related to knowledge, attitudes, beliefs, behaviors, motivations, and barriers that influence breastfeeding practices
- Data useful for assessing if the peer counselor model is a feasible means for increasing exclusive breastfeeding and maintaining breastfeeding for the recommended period of time
- Data related to the barriers and facilitating factors for recruitment and retention of breastfeeding peer counselors
- Data that describes institutional needs for creating a successful peer counseling model and a successful culturally appropriate training curriculum
- Data relevant to the feasibility of using a mobile -based platform to support the peer counselor model for education, counseling and support of mothers
- Data relevant to the feasibility, acceptability and effect size of the BEST4Baby program o Survey data from mothers which includes socio-demographic data; data relevant to breastfeeding and support for breastfeeding; breastfeeding knowledge, attitudes, beliefs, and intentions to continue breastfeeding; and environment influences and factors that support breastfeeding
- Data relevant to the acceptability and use of breastfeeding mobile technology tools
- Names and contact information of subjects recruited to participate in components of the project

Data resulting from querying mothers receiving counseling/support during the pilot testing phase of the project based, for example, on questions related to if and when babies were breastfed exclusively, pre-lacteal feeds given to newborns, when breastfeeding was initiated and when it was stopped, when complementary feeding was initiated.

Indicate who will have access to individually identifiable private information about human subjects AND

Provide information about how the specimens, records, and/or data will be collected, managed, and protected, as well as whether any individually identifiable private information will be collected specifically for the proposed research project:

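### The plan sets out to test behavioural mechanisms but schedules no theory construct between the start of counselling and the outcome, and it calls changes that follow childbirth moderators

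*Combined protocol and SAP*

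**What the plan says.** The Data Analysis section for Month 24 gives two modelling aims. The second is to "test mechanisms underlying behavioral outcomes hypothesized in the conceptual model leveraging social cognitive theory, theory of planned behavior, and social marketing". No construct, instrument, measurement time or mediation method is attached to it. The same section says that "potential moderating variables (e.g., lifestyle changes due to childbirth and behaviors) will be examined", alongside changes from baseline to follow-up.

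On measurement, the Intervention and Data Collection Plan (Months 15-23) states that at six months "research staff will query the mother about present and planned BF practices, environmental influences on breastfeeding, level of community support for BF", plus satisfaction with the programme. Present feeding, which is the outcome, is therefore asked at the same contact as planned feeding, environment and support. For the counselled group, "Visit 1 and 2 will occur prenatally at which time baseline data will be collected", and at those same visits "initial BF education based on appropriate BEST4Baby content will also take place". For the comparison cohort, "We will obtain baseline and six-month post-partum data from a control group of 120 women". The content of baseline is not listed for either group.

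Section II, Sources of Materials, lists "breastfeeding knowledge, attitudes, beliefs, and intentions to continue breastfeeding" among the survey data from mothers, without saying when they are collected. The paragraph on hypothesised outcomes after Primary Aim 2 puts the measurement of intent before project close. The sampling-plan paragraph in section I.a seeks late intent only from mothers who are still breastfeeding.

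**The concern.** A mechanism claim needs a time order: the programme acts, the construct moves, and then the outcome follows. The construct therefore has to be measured after the programme has had a chance to act and before the outcome is known. If intention and perceived support are recorded in the interview that records feeding, a mother who succeeded may report stronger intention and more support because she succeeded. Asking intent only of those still breastfeeding goes further, since the construct is then observed only for one level of a feeding outcome.

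The moderator label raises a related problem. A moderator should be fixed before exposure. Lifestyle changes due to childbirth come after the two prenatal counselling visits and may be altered by them.

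The documents say the pilot data will feed the application for a fully powered trial. A behavioural model that appears confirmed when it has not been tested could be carried into that design.

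**Working it through.** **1. Time order of each construct, as the documents give it**

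| Measure | Stated time | Stated between counselling start and outcome? |
|---|---|---|
| Feeding practice (outcome) | Six-month interview | – |
| Planned practices / intention | Six-month interview; also before project close, from mothers still breastfeeding | No |
| Environmental influences, community support | Six-month interview | No |
| Knowledge, attitudes, beliefs | None given | Not stated |
| Baseline, counselled group | Prenatal visits 1 and 2, where education also begins; content not listed | Not designed as such |
| Baseline, comparison group | Planned; content not listed | – |
| Lifestyle changes due to childbirth | After delivery, hence after the prenatal visits | Post-exposure |

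The visit at 3-5 days gathers data such as when breastfeeding began, and the two-week visit records progress. Neither is described as measuring a theory construct. A baseline score alone cannot show what counselling changed, and a change score from baseline to six months still ends at the outcome interview.

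**2. The plan's own figure**

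The counselled sample is 24 counsellors × 5 mothers = 120, which reproduces. It is a product, not a power calculation: no alpha, power or target difference is given. The point does not depend on it, but it sets the scale of the illustrations below.

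**3. Illustration A: association between construct and outcome (assumed inputs)**

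Assume that the construct has no effect on feeding, but that mothers who succeeded score d SD higher afterwards. Take N = 120, with share p exclusively breastfeeding, in a two-sided 5% two-group t test on 118 degrees of freedom. The non-centrality is d × √(n₁n₂/120), where n₁ = 120p and n₂ = 120 − n₁. Example: p = 0.2 gives n₁ = 24 and n₂ = 96; with d = 0.5 the non-centrality is 0.5 × √19.2 = 2.19, and the probability of significance is 0.58.

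| d | p = 0.2 | 0.3 | 0.4 | 0.5 |
|---|---|---|---|---|
| 0.3 | 0.26 | 0.32 | 0.36 | 0.37 |
| 0.5 | 0.58 | 0.70 | 0.76 | 0.78 |

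The nominal rate is 0.05. This is the rate of a spurious association, not of a false mediation finding, which also requires the group to be linked to the construct.

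**4. Illustration B: two-step mediation test (assumed inputs)**

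Simulation with 120 mothers per group and 4,000 runs per setting. The construct M does not affect feeding Y, but Y raises M by 0, 0.5 or 1.0 SD. Linear models of M on group, and of Y on group and M, are fitted. Mediation is declared when the group term in the first and the M term in the second are both significant at about two-sided 5%.

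| Exclusive breastfeeding, comparison vs counselled | Reverse effect (SD) | M appears to predict Y | False mediation declared |
|---|---|---|---|
| 20% vs 40% | 0 | 5.6% | 0.3% |
| 20% vs 40% | 0.5 | 93.0% | 11.1% |
| 20% vs 40% | 1.0 | 100% | 29.2% |
| 20% vs 50% | 0 | 4.8% | 0.2% |
| 20% vs 50% | 0.5 | 94.4% | 19.4% |
| 20% vs 50% | 1.0 | 100% | 56.8% |

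In the four rows with a reverse effect, about 5% to 17% of the group difference appears to be mediated, although none is.

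**The case against.** The strongest reply is that the documents are silent on timing rather than wrong about it. Baseline data are planned in both groups, their content is never listed, and change from baseline to follow-up is to be examined. Attitudes and intentions may well be in the baseline survey. This stands against a stronger reading that a reader might infer, namely that all the constructs are first measured after counselling, in the six-month interview. The documents do not say so. Attitudes, self-efficacy and perceived control are not listed in that interview at all. The reply does not rescue the mechanism test, because a baseline score does not supply the missing measurement between counselling and outcome.

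Interim data are also fuller than two surveys suggest. Counsellors complete a form at each visit that may include feeding status, and the Timeline mentions follow-up of feeding status at defined intervals. That concerns the outcome rather than the constructs, so it does not close the gap, though it helps with a fix.

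On moderators, the plan says only that they will be examined. A reader might infer that effect estimates stratified by post-exposure variables are planned and will be biased. No interaction or stratified estimate is specified, so what remains is a wrong label that invites such an analysis.

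Finally, this is a non-randomised exploratory pilot, with one clause on mechanisms and no decision rule tied to it. That limits the consequences, but correcting the wording costs almost nothing.

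**Conclusion.** The point holds in this form: as written, the planned mechanism test cannot tell a mediator from a consequence. Every theory construct with a stated time is collected with the outcome or later, the others have no stated time, and nothing is scheduled in between. Calling childbirth-driven changes moderators is incorrect on the plan's own sequence of visits. Both conclusions rest on the text alone.

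The size is illustrative only. The reverse effects and feeding rates are assumptions; none comes from the documents. A reader might take the 26% to 37% and 58% to 78% in Illustration A as the chance of falsely confirming the behavioural model. They are not: they describe an association between construct and outcome. The two-step figures in Illustration B are closer to that risk, and they vary widely with the assumed inputs.

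**What to change.** In the Month 24 Data Analysis section:

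- Replace the commitment to test mechanisms with a statement that constructs measured at six months will be reported as exploratory correlates of feeding.
- Limit effect modifiers to variables fixed before the first counselling contact, such as age, parity, education and prior breastfeeding.
- Treat childbirth-related changes as post-exposure variables.

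These are wording changes and cost next to nothing.

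Optionally, collect a short construct set before the first education contact and again at the existing two-week visit. Relate the two-week score to six-month feeding, adjusting for the baseline score and for feeding status up to two weeks, because early feeding can already drive the two-week score. Call this an exploratory predictor analysis within the counselled group. It is not a mediation test, since without the comparison group it cannot show that the programme moved the construct. The cost is a few items on data sheets that are still to be developed. The drawback is that the two-week items would be collected by the counsellors delivering the programme and so be open to courtesy bias.

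### The dosage index used to explain six-month feeding lists satisfaction, which appears to be asked in the same interview as feeding, and counts requested contact through six months, so a dose slope can arise with no programme effect

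*Combined protocol and SAP*

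**What the plan says.** All references are to the combined protocol and SAP, Specific Aim 2.

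- **The models (Month 24, Data Analysis).** The only regressions named are exact logistic models. One sentence asks whether level of participation "is associated with an increase in optimal breastfeeding practices". The next, whose outcome is continued breastfeeding at six months, says the models will "examine the effect of BEST4Baby dosage, using the dosage index based on pilot test usage and self-report data as independent variables". A third sentence gives the odds of exclusive, mixed and substitute feeding "as a function of BEST4Baby dosage based on utilization and process data".
- **The index (same section).** "Dosage measures will include time/counts of activity, intensity, engagement, and satisfaction". No weights, measurement window or cut-off date are given. Usage data are to include "approximate time spent in use of application during home visits) in the follow-up interviews". The index is to be calculated "and used as a covariate in subsequent analyses".
- **When things are measured (Intervention and Data Collection Plan).** App usage is recorded at each visit. Mothers' overall satisfaction with the programme is asked at six months postpartum, in the same query as present feeding.
- **Contact (New Mothers; Intervention and Data Collection Plan).** Mothers receive "follow-up visits from peer counselors during the 6 months post-delivery". The minimum is nine visits, timing after two weeks is by agreement, and breastfeeding mothers may ask for extra visits or phone the counsellor with concerns.
- **The effect size (Comparison Cohort; objective 2.2).** "To enable effect and sample size calculations, an appropriate comparison cohort will be used". This is a contrast of 120 counselled with 120 comparison mothers.

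**The concern.** A dose-response model is informative only if dose is settled before the outcome, or at least is not shaped by it. Two parts of this index can be shaped by it.

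First, a mother asked about satisfaction in the interview that records her feeding already knows how feeding went. If mothers for whom it went well rate the programme higher, the index rises with the outcome whatever the programme did.

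Secondly, a mother who has stopped exclusive breastfeeding (EBF) but still breastfeeds may ask for more help. Those contacts come after the change in feeding, yet count as dose. This pushes the EBF slope downward.

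Exact inference does not help: it deals with small numbers, not with a predictor that depends on the outcome. A larger sample makes a wrong slope more certain. The Conclusion says the findings will support an application for a fully powered trial of counselling and mobile tools, so a spurious slope in either direction could mislead that design.

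**Working it through.** **The plan's own figure.** 24 counsellors × 5 mothers = 120 counselled, as stated. No alpha, power or expected dose-response is given, so there is nothing further to reproduce. I assume a two-sided 5% test, that is 2.5% in each direction.

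**Assumed inputs.** No programme effect; n = 120; four equally weighted, standardised measures. Six-month EBF is 40% (assumed) or 20% (the only six-month rate in the protocol, in Significance); continued breastfeeding is 90% (assumed). The documents give no strength for any of the behaviour below.

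**Satisfaction.** Let p be the outcome proportion and d the satisfaction difference in SD between mothers with and without the good outcome.

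- Correlation of satisfaction with outcome: r_s = d√(p(1−p)) / √(1 + d²p(1−p)).
- V is the variance of the sum of the four measures: 4 if uncorrelated; 4 + 2×0.5 = 5 if two of the other three correlate 0.5; 4 + 6×0.5 = 7 if all three do.
- Expected test statistic: z = r_s√119/√V. Chance of a false positive slope: P(Z > 1.96 − z).

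Example, p = 0.4, d = 0.5: r_s = 0.245/√1.06 = 0.238. With V = 4, z = 0.238 × 10.91/2 = 1.30 and P(Z > 0.66) = 25%. With V = 5, z = 1.16, giving 21%. With V = 7, z = 0.98, giving 16%.

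False positive slope (%) for d = 0.2 / 0.5 / 0.8:

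| Outcome | V = 4 | V = 5 | V = 7 |
|---|---|---|---|
| EBF 40% | 8 / 25 / 51 | 7 / 21 / 43 | 6 / 16 / 32 |
| EBF 20% | 6 / 19 / 38 | 6 / 16 / 32 | 5 / 12 / 24 |
| Continued 90% | 5 / 12 / 25 | 5 / 11 / 21 | 4 / 9 / 16 |

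For V between 4 and 5, simulation gives about 7–8 / 20–25 / 43–53 (EBF 40%) and 5 / 11–12 / 19–25 (continued 90%), in line with the formula.

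**Requested visits, EBF 40%.** Every mother gets nine visits, plus unrelated requests (Poisson, mean 1), plus requests after EBF stops at a rate of e per full 26 weeks. With a constant stopping rate, −ln 0.4 = 0.916. The mean share of the period left after stopping is 1 − 0.6/0.916 = 0.345 (variance 0.127), or 0.345/0.6 = 0.575 among those who stop. They therefore average 0.575e more visits.

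- Size of the (negative) correlation with EBF: r_v = 0.575e × 0.490 / √(1 + 0.345e + 0.127e²), which is 0.067, 0.128, 0.232 for e = 0.25, 0.5, 1.
- As one of four measures (V = 4): z = 0.37, 0.70, 1.27, so a false inverse slope in 6%, 10%, 24%. Simulation gives about 6 / 11 / 23%. With V = 7 the formula gives 5 / 8 / 16%.
- As a raw visit count: z = 0.73, 1.40, 2.53, so 11%, 29%, 72%. Simulation gives 10 / 28 / 73%.

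**Both together.** With d = 0.5 and e = 1, r_s and r_v are 0.238 and 0.232 in opposite directions. The net z is (0.238 − 0.232) × 10.91/2 = 0.03. Simulated total rejection is about 4%, which is nominal: the two biases cancel.

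**The case against.** Several points on the other side stand.

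- **The text does not say outright that the six-month item feeds the index.** The list of dosage measures does not say whose satisfaction is meant or when it is taken. The Project Summary has staff visiting mothers for feedback, and the Timeline has follow-up at defined intervals. But the six-month query is the only measurement of mothers' satisfaction described, so it is the natural source unless the plan says otherwise.
- **The EBF sentence is narrower.** It bases dosage on utilisation and process data, so satisfaction bears most clearly on the continued-breastfeeding model.
- **The planned index is a composite.** The large inverse-slope figures (10 / 28 / 73%) apply only if dose is a raw visit count. In a four-part index they fall to about 6 / 11 / 23%.
- **The outcome is exploratory.** The primary outcome concerns counsellor training and capability, and the secondary is EBF at six months. Dose-response is neither.

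A reader might also infer that the continued-breastfeeding model must be biased upward because only women still breastfeeding can request visits. That needs a narrow reading of a label which objective 2.2 applies to all 120 counselled women, so I do not rely on it.

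**Conclusion.** The concern holds in limited form. As written, the models can return a dose slope, positive or inverse, when the programme has no effect, and the plan describes one such slope as an effect of dosage. Under the assumptions shown, the satisfaction route raises the false positive rate from 2.5% to roughly 20–25% for a 0.5 SD difference at 40% EBF, and to about 11–12% for continued breastfeeding at 90%. The requested-visit route gives a false inverse slope in about 11% at e = 0.5. These rates show direction and possible size and are not predictions. The net bias could be close to zero.

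Two stronger readings are not supported. One is that the 120-versus-120 effect size is compromised: as described, that contrast does not use the index. The covariate wording leaves the door open but commits to nothing. The other is that a missed true benefit has been shown: with no programme effect, the downward error is a spurious inverse slope, not a false negative.

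Severity is low to moderate.

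**What to change.** 1. Remove satisfaction and other six-month self-report from the index used in the regressions, and report them as acceptability. Build the index from protocol-scheduled visits and per-visit app usage (Intervention and Data Collection Plan; the per-visit form in section VI). Keep mother-requested contacts out of the index and report them separately. For this, have the visit form record the visit date and whether the mother asked for the visit; the protocol does not say that it does.
2. Report dose results as associations among counselled mothers. Replace the causal wording of the continued-breastfeeding sentence with the associational wording of the sentence before it.
3. State that the index is not a covariate in the counselled-versus-comparison estimate.

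**Cost.** This is plan wording plus two fields on a form still to be developed. Usage that only the mother can report, such as material viewed between visits, leaves the model. If nearly every mother receives the scheduled visits, the index will vary mainly through app usage. Confounding by motivation remains, and scheduled visits missed after a mother stops feeding would still enter the index; step 2 labels these limits and does not remove them.

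### The exact logistic regression of breastfeeding on dosage makes no allowance for counsellor or cluster, so its p-values and intervals are too optimistic where dosage and outcome both vary by counsellor

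*Combined protocol and SAP*

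**What the plan says.** The Month 24 Data Analysis section proposes to "apply exact logistic regression models to determine if the level of participation in BEST4Baby is associated with an increase in optimal breastfeeding practices". The dosage model is then described as "using the dosage index based on pilot test usage and self-report data as independent variables", with continued breastfeeding at six months as the outcome. The section adds: "We will calculate odds of exclusive breastfeeding, mixed feeding and use of milk substitutes at follow-up as a function of BEST4Baby dosage".

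On the index itself: "Dosage measures will include time/counts of activity, intensity, engagement, and satisfaction". It is a composite ("These combined process measures will be calculated as a" dosage index), to be "used as a covariate in subsequent analyses" and to "serve as an independent variable for multivariate modeling". Separately, "potential moderating variables (e.g., lifestyle changes due to childbirth and behaviors) will be examined".

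The plan gives no scale, weights or categories for the index, and no list of covariates for the exact model. It does not say whether comparison mothers enter that model, or why exact rather than ordinary logistic regression was chosen. The only other methods named for Aim 2 are crosstabs and chi-square procedures.

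The structure of the counselled group is stated elsewhere. Objective 2.2 assigns five mothers to each of 24 counsellors. The description of the subject population (Risks to Human Subjects) places four counsellors in each of six clusters. Neither level appears in the analysis section.

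**The concern.** Mothers who share a counsellor share her skill, her persistence and her use of the app. Their feeding outcomes are likely to be correlated, and so are their dosage values, because app time and visit intensity partly reflect the counsellor. An exact test that pools all mothers takes every rearrangement of outcomes across the 120 as equally likely under the null hypothesis. That is not so when outcomes cluster. If dosage clusters too, the spread of the dosage statistic is understated, so p-values are too small and intervals too narrow.

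At stake is the reading of the dose-response result. The Conclusion of the research plan says that the findings will support an application for a fully powered trial. An overstated association between dosage and breastfeeding would feed into that design.

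A second issue depends on choices that the plan leaves open. Exact inference on one coefficient conditions on the observed sufficient statistics of all the others. If one of those belongs to an unrounded continuous index, almost no other arrangement of outcomes reproduces it.

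**Working it through.** **Structure.** 24 counsellors × 5 mothers = 120, which reproduces the plan's figure. 4 counsellors × 5 mothers = 20 per cluster, and 6 × 20 = 120. The plan states no ICC, outcome rate or dosage distribution; all such values below are assumptions.

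**Approximate size of the effect.** For a slope, the variance inflation from ignoring groups of size m is roughly 1 + (m − 1) × ICC(outcome) × ICC(dosage). The actual two-sided error at a nominal 5% is then 2 × Φ(−1.96/√inflation). With m = 5:

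| ICC outcome | ICC dosage | Inflation | Actual error |
|---|---|---|---|
| 0.05 | 0.3 | 1 + 4 × 0.015 = 1.06 | 5.7% |
| 0.05 | 1.0 | 1 + 4 × 0.05 = 1.20 | 7.4% |
| 0.1 | 0.3 | 1 + 4 × 0.03 = 1.12 | 6.4% |
| 0.1 | 1.0 | 1 + 4 × 0.10 = 1.40 | 9.8% |
| 0.2 | 0.3 | 1 + 4 × 0.06 = 1.24 | 7.8% |
| 0.2 | 1.0 | 1 + 4 × 0.20 = 1.80 | 14.4% |

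**Simulation of the test.** 24 groups of 5, no true dosage effect, outcome rate 20% or 50%, ICC of dosage 0.3 or 0.7, outcome ICC set on the logit scale. Each scenario had 2,000 runs with 199 permutations per run. The Monte Carlo standard error at 5% is √(0.05 × 0.95/2000) = 0.5 percentage points.

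| Outcome ICC | Rejections ignoring counsellor |
|---|---|
| 0 | 4.8% to 5.6% |
| 0.05 | 5.2% to 6.0% |
| 0.1 | 5.2% to 8.1% |
| 0.2 | 7.4% to 9.7% |

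The same exact test stratified by counsellor rejected in 3.9% to 5.8% of runs across these scenarios. With dosage wholly shared within counsellor, outcome ICC 0.1 and a 50% outcome rate, the unstratified test rejected in 9.3%; the stratified test never rejected, because no within-counsellor information remains.

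Taken with further runs, the working ranges are about 5% to 7% at ICC 0.05, 6% to 9% at 0.1 and 7% to 13% at 0.2. They sit slightly below the formula because an ICC on the logit scale is smaller on the observed scale. The low ends apply when dosage is little shared within counsellor: one scenario at ICC 0.1 stayed at 5.2%, within simulation error of nominal.

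**Cluster level.** If dosage were wholly shared within a cluster of 20, the inflation would be 1 + 19 × ICC: 1.19, 1.95 and 2.90 at ICC 0.01, 0.05 and 0.10. These are upper bounds for the dosage slope.

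**The conditional point.** Enumeration with 20 mothers and 6 events gives C(20,6) = 38,760 arrangements. The number of distinct values left for the tested statistic was:
- index alone, two decimals: 14,498;
- plus a binary covariate: 3,730;
- plus a second continuous covariate, two decimals: 7;
- plus a second continuous covariate, unrounded: 1. The p-value is then 1 and no finite interval exists.

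At 120 mothers, with an integer index from 0 to 100 as sole predictor, the exact distribution had 612, 945 and 1,350 support points for 12, 24 and 60 events, each computed in under 3 seconds. Stratified by counsellor it had 1,029 points, in 0.06 seconds. With 120 + 120 mothers, rounded dosage as covariate (zero in comparison mothers) and group tested, the group statistic kept roughly 30 to 50 possible values.

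**The case against.** The strongest reply is that this is an exploratory pilot. Exclusive breastfeeding is a secondary outcome, the dosage model is one association analysis, and the ICCs are assumed. At an ICC of 0.05 the excess error is small, and it vanishes if dosage varies mainly between mothers of the same counsellor. That stands, and it limits the severity. It does not remove the point: the plan offers no reason to expect independence, and the correction is cheap.

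A reader might also infer three stronger claims, none of which the documents support.

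- That the dosage estimate cannot be computed. The only predictor named for the exact model is the index, its scale is never stated, and with the index alone, with discrete covariates or with rounded values the exact analysis is non-degenerate. Degeneracy needs an unrounded index conditioned on while another coefficient is tested. The references to a covariate role and to multivariate modelling permit that model but do not specify it. Nor does the plan assign the counselled-versus-comparison contrast to it.
- That enumeration over 120 to 240 mothers is impractical. Brute-force listing would be, but a counting recursion finishes in seconds.
- That exact methods cannot handle clustering. Stratifying by counsellor kept the error near nominal. The real limits are that exact logistic regression has no random effect or robust variance, and that stratifying discards all dosage variation between counsellors.

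**Conclusion.** The concern holds in this form: the only regression named for Aim 2 treats mothers as independent although five share each counsellor and 20 share each cluster. Where dosage and outcome both vary by counsellor, a nominal 5% test has a true error of about 5% to 7% at ICC 0.05, 6% to 9% at 0.1 and 7% to 13% at 0.2. In interval terms, an inflation of 1.40 (ICC 0.1, dosage wholly shared) means that a correct interval would be √1.40 = 1.18 times as wide. These figures rest on assumed ICCs, outcome rates of 20% and 50%, and an assumed dosage distribution, and they cover the counsellor level only; correlation within cluster would add to them.

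The degeneracy point is secondary and conditional. It arises only if an unrounded index is a covariate alongside other predictors, in which case the other coefficients are not estimable. Overall this is a change that should be made, at modest severity for a pilot.

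**What to change.** In the Month 24 Data Analysis section, replace exact logistic regression for the dosage model with one of:
- a logistic model with counsellor random intercepts and cluster as a fixed or random effect;
- GEE with a small-sample correction.

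Use Firth penalisation if a feeding category is sparse. State the scale and scoring of the index, the covariates, and whether comparison mothers are included.

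Keep exact methods for sparse two-way tables, or as a sensitivity analysis of a single scored index stratified by counsellor. Note there that this version has no information if dosage varies only between counsellors.

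The cost is analysis wording only, with no new data: counsellor and mother already carry study identification numbers on the visit forms, and cluster of residence is retained. The downside is reliance on approximate p-values with 24 counsellors and six clusters, and slightly wider intervals.
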